10 SAFETY ANALYSES

10.1 Overview of Safety Analysis Methods

All safety analyses will be performed using all participants who were randomized. Descriptive p-values comparing the study arms will be provided on most safety table summaries and will be obtained using chi-square tests or Fisher's exact tests (in the case of small numbers of events) for binary outcomes. If the number of events allow, a 2-sided Cochran Mantel-Haenszel test controlling for strata defined by site and baseline urge IE group will be used to obtain the p-values.

10.2 Adverse Events

Per the protocol, participants were asked to report any adverse events from initiation of treatment through 12 months follow-up. All adverse events were collected on an adverse event log and coded using MedDRA (V17.0).

Postoperative complications noted as adverse symptoms and events in the ESTEEM manual of procedures (MOP) (see table below) will be proactively reviewed and reported. ESTEEM complications are divided into “adverse symptoms” and “adverse events”. To help standardized the data collection process for complications, adverse symptoms and events will be captured as follows:

Adverse symptoms will be captured using either an active approach using validated questionnaires or an open-ended approach.

- a. Active capture for adverse symptoms: Specific patient-reported adverse symptoms will be identified by responses on validated questionnaires (denoted by * in table below). These 3 adverse symptoms include a patient report of new or worsening: 1) pelvic/vaginal pain, 2) sensation of incomplete bladder emptying (based on UDI responses) and 3) dyspareunia (based on PISQ-IR response). These are captured at 3, 6, and 12 months. To aid with retrospective collection of these AEs, the DCC will provide each site with a report listing longitudinal responses to the applicable UDI and PISQ-IR questions for participants who reported one of these symptoms at 3-12 months. The clinical site will report these adverse symptoms on the adverse events CRF per the usual process described in the MOP.

The clinical site will be responsible for reviewing the UDI and PISQ-IR responses for these 3 items and identifying any new or worsening symptoms. Once a new or worsening symptom is identified, the clinical site will track these adverse symptoms per the usual process in the MOP. Sites should review the UDI and PISQ-IR CRFs at the time the participant completes them so that any additional information needed to complete the adverse event CRF can also be collected at that time.

- b. Open-ended capture for adverse symptoms: 2 adverse symptoms will be captured using the open-ended approach because they are not captured in any of the validated questionnaires administered in ESTEEM. These include: 1) New/worsening partner dyspareunia and 2) New/worsening constipation. Using the open-ended approach, symptoms are captured if reported by the participant.

Adverse events will be captured using the standard capture for AEs as described in the MOP and manually reviewed to determine which events meet the criteria for post-operative complication listed in the table below. This is an open-ended capture approach using chart review, physician report, or patient report corroborated by medical documentation.

Postoperative complications	
Adverse symptom	Definition

Network

Protocol ESTEEM Statistical Analysis Plan

New/worsening abdominal/genital pain at or beyond 3 month visit	UDI item N captured at 3, 6, 12 months and per patient report, chart review, physician report
New/worsening dyspareunia at or beyond 3 month visit	PISQ item C5 captured at 3, 6, 12 months and per patient report, chart review, physician report
New/worsening report of difficulty emptying bladder at or beyond 3 months	UDI item J captured at 3, 6, 12 months and per patient report, chart review, physician report
New/worsening partner dyspareunia at or beyond 3 month visit	Per patient report, chart review, physician report
New/worsening urge incontinence at or beyond 3 month visit	UDI item C captured at 3, 6, 12 months and per patient report, chart review, physician report
Adverse Event	
Postop need for catheter and/or ISC at or beyond 2 weeks	Captured by chart review, physician report, exam, or patient report corroborated by medical documentation
Vaginal mesh exposure	Captured by chart review, physician report, exam, or patient report corroborated by medical documentation
Vaginal mesh erosion into organ	Captured by chart review, physician report, exam or patient report corroborated by medical documentation
Other wound healing problems >6 weeks	Captured by chart review, physician report, exam or patient report corroborated by medical documentation
New/worsening vaginal infection	Captured by chart review, physician report, exam, or patient report corroborated by medical documentation
Urinary tract infection beyond 2 weeks	UTI based on clinical judgment or confirmation of culture proven, also includes empiric antibiotic treatment for symptoms thought to be due to UTI, or patient report corroborated by medical documentation. If a culture is sent that turns out to be negative, this would not be classified as a UTI. Captured by chart review, physician report, or patient report corroborated by medical documentation
Other infection possibly related to intervention (sling and/or BPTx)	Infection diagnosed using clinical or radiologic indicators – not including vaginal infection, UTI Captured by chart review, physician report, or patient report corroborated by medical documentation
Non-study health care provider visit due to complication related to intervention (sling and/or BPTx)	Captured by chart review, physician report, or patient report corroborated by medical documentation

Emergency room visit due to complication related to intervention (sling and/or BPTx)	Captured by chart review, physician report, or patient report corroborated by medical documentation
Hospital readmission related to intervention (sling and/or BPTx)	Captured by chart review, physician report, or patient report corroborated by medical documentation
Reoperation related to surgery (any return to OR for issue related to intervention (e.g. recurrent SUI, UUI/OAB)	Captured by chart review, physician report, or patient report corroborated by medical documentation
An adverse event that is “unexpected” and “possibly, probably or definitely related”	Captured by chart review, physician report, or patient report corroborated by medical documentation

AEs will be listed and summarized by system organ class and preferred event term. Summaries will be of the number of events and number of individuals experiencing events by treatment group and will be created for all AEs, and AEs by severity. Any events starting outside of the reportable timeframe will be included in separate listings and will be excluded from summary tables. If a complete onset date is unknown and it cannot be confirmed that the event occurred during this time period, then the event will be considered a treatment-emergent AE.

Adverse events will be individually reviewed to determine if they meet the conditions specified for each post-operative complication. The review will be conducted via keyword searches through reported event terms and comment for specific events (e.g. vaginal mesh exposure, ER visits, etc.) and by preferred term and system/organ class for more general complications (e.g. new/worsening vaginal infection, other infections, etc.). Worsening symptoms will be assessed by identifying worsening responses (compare to baseline) to the specific patient-questionnaire items identified at post-baseline collection times. Post-operative complications will be summarized by complication type. Summaries will be the number of individuals experiencing complications by treatment group.

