Due to limitations in how to best define successful treatment of MUI, the investigators had extensive discussion around whether an objective, subjective, or composite outcome would be best for this trial. The team agreed that the primary outcome must remain true to the clinical question and be clinically relevant in capturing both potential benefit and harm of both the control and the intervention for this trial. It is critical that the outcome is meaningful from the patient perspective and will be able to capture OAB improvement, worsening, or no change in symptoms. The team discussed using bladder diary, patient global impression, or OAB PROs. Arguments against each of these were based on the following rationale:

1. Problems with using bladder diary as primary outcome:

a. Diary does not capture a meaningful patient outcome- It is becoming clear that typical clinical trial endpoints such as reduction in IEs, voided volumes, etc do not capture what is meaningful to patients. Counting IEs on diary likely does not capture what is important to a patient (e.g. having 3 large urge leaks a day may be more bothersome than having 20 small stress leaks or having 20 urgency associated voids may be more bothersome than having 1 UUI episode). In addition, diary IEs do not correlate perfectly with patient satisfaction.⁵³ Finally, bladder diaries have been shown to be less reliable in women with MUI, particularly for the SUI component.⁵⁴

b. Diary cutoffs to define improvement for MUI are unknown-What percent improvement for the SUI component and for the UUI component is clinically important for a woman with MUI? Any cutoffs chosen would be arbitrary.

c. Using IEs on bladder diary as a primary outcome would require a minimum number of IEs (approximately 3-4 IE/3days) at baseline to be able to detect a change. The protocol team felt that setting such strict inclusion criteria would be too limiting to allow recruitment of a good range of MUI severity (see Inclusion Criteria, Section 4.2).

For all of these reasons, the team decided against using bladder diary IEs as the primary outcome and to instead focus on measures that can capture outcomes from the patient perspective.

2. Problems with using global impression measure as primary outcome

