4.2. Inclusion Criteria

- 1) Presence of both SUI and UUI on bladder diary; and ≥ 2 IEs/3 days
 - a) ≥ 1 Stress IE/3 day diary
 - b) ≥ 1 Urge IE/3 day diary
- 2) Reporting at least "moderate bother" from UUI item on UDI
"Do you usually experience urine leakage associated with a feeling of urgency, that is a strong sensation of needing to go to the bathroom?"
- 3) Reporting at least "moderate bother" from SUI item on UDI
"Do you usually experience urine leakage related to coughing, sneezing, or laughing"
- 4) Diagnosis of SUI defined by a positive cough stress test (CST) or UDE within the past 18 months
- 5) Desires surgical treatment for SUI symptoms
- 6) Urinary symptoms ≥ 3 months
- 7) Subjects understand that BPTx is a treatment option for MUI outside of ESTEEM study protocol (see Section 5.3 for Rationale)
- 8) Urodynamics within past 18 months

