9.2 Efficacy Variables

Primary and secondary efficacy variables as well as exploratory and safety outcomes are described in the table below.

Variable	Type	Definition
Primary Outcomes		
Change from baseline in UDI Total Score at 12 months	Continuous	The Urogenital Distress Inventory-Total Score will be computed at baseline and 12 months (and 3 and 6 months) using the standard scoring algorithm. Specifically, the instructions are to sum the Stress, Irritative, and Obstructive subscales of the UDI (see below). If any subscale scores are missing, then no Total score will be calculated. The outcome will then be computed as the difference in Total score at 12 months (and 3 and 6 months) and the Total score at baseline. If data for an assessment time point are missing, the outcome variable will be coded as missing.
Secondary Outcomes		
Change from baseline in UDI Stress Score at 12 months	Continuous	The Urogenital Distress Inventory-Stress Score will be computed at baseline and 12 months (and 3 and 6 months) using the standard scoring algorithm. Specifically, the instructions are to average responses across questions D and F and their respective sub-questions (0=No or Yes and Not at all; 1=Yes and Slightly; 2=Yes and Moderately; 3=Yes and Greatly), and then multiply by 100/3. If any responses are missing, then the score will be calculated as the average of the non-missing responses. The outcome will then be computed as the difference in score at 12 months (and 3 and 6 months) and the score at baseline. If data for an assessment time point are missing, the outcome variable will be coded as missing.
Change from baseline in UDI Irritative Score at 12 months	Continuous	The Urogenital Distress Inventory-Irritative Score will be computed at baseline and 12 months (and 3 and 6 months) using the standard scoring algorithm. Specifically, the instructions are to average responses across questions A, B, C, G, H, and I and their respective sub-questions (0=No or Yes and Not at all; 1=Yes and Slightly; 2=Yes and Moderately; 3=Yes and Greatly), and then multiply by 100/3. If any responses are missing, then the score will be calculated as the average of the non-missing responses.

Network

Protocol ESTEEM Statistical Analysis Plan

Variable	Type	Definition
		The outcome will then be computed as the difference in score at 12 months (and 3 and 6 months) and the score at baseline. If data for an assessment time point are missing, the outcome variable will be coded as missing.

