High Voiding Frequency at 12 months	Dichotomous (Yes/No)	
The total number of daytime and nighttime voids will be taken from the bladder diary and summed and divided by the number of diary days (≤ 3) to get a voiding frequency. The indicator for high frequency at 12 months (and 6 months) will be defined for each subject as follows:
 
If > 8 voids/24 hours at time x: Yes If ≤ 8 voids/24 hours at time x: No
 
If data for the assessment time point are missing, the high frequency indicator will be coded as missing.
 
The variable is summarized as the percentage of participants with indicator equal to “Yes” among all non-missing indicators.

Dryness at 12 Months (Diary)	Dichotomous (Yes/No)	
The total number of incontinence episodes will be taken from the bladder diary and summed and divided by the number of diary days (≤ 3) to get an average daily number of episodes. The indicator for dryness at 12 months will be defined for each subject as follows:
 
If 0 episodes/24 hours at time x: Yes If > 0 episodes/24 hours at time x: No
 
If data for the assessment time point are missing, the dryness indicator will be coded as missing. The variable is summarized as the percentage of participants with indicator equal to “Yes” among all non-missing indicators.

Dryness at 12 Months (UDI-LF)	Dichotomous (Yes/No)	
The response to questions C (Do you experience urine leakage related to the feeling of urgency?) and D (Do you experience urine leakage related to physical activity, coughing, or sneezing?) will be taken from the UDI-LF. The indicator for dryness at 12 months will be defined for each subject as follows:
 
If question C = No and question D = No at time x: Yes If question C = Yes or question D = Yes at time x: No
 
If data for the assessment time point are missing, the dryness indicator will be coded as missing. The variable is summarized as the percentage of participants with indicator equal to “Yes” among all non-missing indicators.

Network

Protocol ESTEEM Statistical Analysis Plan

Variable	Type	Definition

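### UDI item C has a ceiling imposed by eligibility, so the questionnaire route under-counts worsening urge incontinence in the safety table by an amount that cannot be judged from the plan

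*SAP*

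**What the plan says.** The complications table in SAP 10.2 includes "New/worsening urge incontinence at or beyond 3 month visit", defined as "UDI item C captured at 3, 6, 12 months and per patient report, chart review, physician report". The closing paragraph of the same section gives the rule for worsening: "Worsening symptoms will be assessed by identifying worsening responses (compare to baseline) to the specific patient-questionnaire items identified at post-baseline collection times". Results are summarised as the number of individuals with each complication by treatment group. SAP 5.3 and 10.1 make all randomized women the safety population, and no at-risk denominator is stated for any row.

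SAP 9.2 identifies the item: "questions C (Do you experience urine leakage related to the feeling of urgency". In the UDI-irritative entry, which includes question C, the scoring is "0=No or Yes and Not at all; 1=Yes and Slightly; 2=Yes and Moderately; 3=Yes and Greatly".

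Inclusion criterion 2 (Protocol 4.2, repeated in SAP 4.2.1) is "Reporting at least 'moderate bother' from UUI item on UDI". Protocol Table 11 shows one baseline UDI serving both eligibility and outcome.

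The capture text earlier in SAP 10.2 names three symptoms for active questionnaire review (pain, incomplete emptying, dyspareunia) and two for open-ended capture (partner dyspareunia, constipation). Urge incontinence is in neither list.

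**The concern.** A worse-than-baseline rule needs room above baseline. Eligibility removes nearly all of it for this item: every eligible woman starts in the top two of four levels. Those at the top cannot be recorded as worse on the item, yet they remain in the count as women without the complication.

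Persistent or worse urge symptoms after the sling are the risk that Protocol 2.8 singles out, and Protocol 2.9 lists what happens to OAB symptoms after surgery as a gap that the trial should close. A low count in this row could be read as reassurance when part of it comes from the scale. The three symptoms named for active review have no comparable minimum bother score in the eligibility criteria.

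**Working it through.** The plan states no rate, power or sample size for this outcome, so there is no planned figure to reproduce. The check has four steps.

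**1. Room on the scale.** An unrestricted 0-3 item allows six upward moves: 0 to 1, 0 to 2, 0 to 3, 1 to 2, 1 to 3 and 2 to 3. With baseline limited to 2 or 3, one remains: 2 to 3. A *new* case would need a baseline response without urge leakage, which criterion 2 excludes.

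**2. Share that the item cannot record.** Let p be the baseline share scoring 3, and r the risk of true worsening at score 3 relative to score 2. The share of true worsening invisible to the item is

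p·r / (p·r + 1 − p).

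With r = 1 this equals p. It exceeds one half when p > 1/(1 + r), that is above 67% for r = 0.5, 50% for r = 1 and 33% for r = 2.

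**3. Effect on the reported rate.** With r = 1, and if every true worsening from score 2 registers and nothing else does, item rate = true rate × (1 − p). The share p is not in the documents and is assumed at 20%, 50% or 80%. The true rates are scenarios from Protocol 2.5: 19% worsened UUI at 12 months in one sling trial's subset of 83 women with urodynamic MUI, and 4-10% new or worsened UUI at 1 year in another sling trial. Counts use 472/2 = 236 women per arm.

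| Assumed share at 3 | True 4% shows as | True 10% shows as | True 19% shows as | Women per arm at 19% (true: 236 × 0.19 = 44.8) |
|---|---|---|---|---|
| 20% | 3.2% | 8.0% | 0.19 × 0.8 = 15.2% | 35.9 |
| 50% | 2.0% | 5.0% | 0.19 × 0.5 = 9.5% | 22.4 |
| 80% | 0.8% | 2.0% | 0.19 × 0.2 = 3.8% | 9.0 |

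**4. Allowing for the report routes.** If patient, chart and physician reports recover a fraction c of the ceiling cases, the missed share falls to p(1 − c). At an assumed c = 0.5 it is 10%, 25% and 40% for p of 20%, 50% and 80%. The documents give no basis for choosing c.

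**The case against.** **Item C is not the whole definition.** The table also admits patient report, chart review and physician report, and SAP 10.2 has adverse events reviewed individually. A woman at 3 who reports worse leakage can enter the table. This stands, and it limits the figures above to the item route. It does not close the gap: the symptom is in neither capture list, and the SAP does not say how a report combines with the item rule. SAP Attachment 16.1 also asks that adverse events that could be treatment failures be moved to the additional therapies form where applicable, so some reported worsening may leave the log under review. The table derives from a manual of procedures that is not available here, and it may say more.

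**Worsening is measured elsewhere.** UDI-irritative score, diary urge episodes, OAB-q, retreatment and sling revision for worsened OAB are all analysed (SAP 9.2). So the trial is not blind to worsening. But the scores and diary counts are analysed as mean change, where women who improve can offset women who worsen, and the last two count only women who received treatment. Individual worsening is planned for voiding frequency (SAP 9.5.1), not for urge leakage.

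**The comparison between arms is protected.** Allocation is randomized and stratified by urge-episode severity, and safety p-values are descriptive. This is right. The concern is mainly with the absolute count.

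**Stronger readings that the documents do not support.**
- A reader might infer that most worsening cannot register. That needs a baseline share at 3 above roughly 33-67%, depending on r, and the share is not given.
- The 25% in Protocol 2.5 is worsened urgency, not urge leakage, and should not be passed through item C.
- The Protocol 3.4.1.a statement that the outcome "will be able to capture OAB improvement, worsening, or no change in symptoms" concerns the primary outcome, so this row does not contradict it.

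**Conclusion.** The ceiling follows from the text. For an eligible woman, one upward move out of six is left on item C, a woman at 3 cannot be a case on it, and *new* has no content. She is still counted among those without the complication.

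The size is conditional. Under independence, the item route misses exactly the baseline share at 3, and a true 19% would appear as 15.2%, 9.5% or 3.8% at assumed shares of 20%, 50% or 80%. Recovery through reports would shrink the loss by an unknown amount. The 19% and 4-10% rates come from other trials and are scenarios, not predictions for this one.

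Two further assumptions apply. The eligibility item is taken to be item C: both describe urge leakage on the same UDI, although the quoted wordings differ. The baseline used for comparison is taken to be the one that met eligibility; SAP 7.9 has assessments repeated when surgery is delayed beyond 3 months, so an occasional baseline below 2 is possible.

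The row is descriptive. The primary and secondary efficacy analyses are unaffected.

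**What to change.** In SAP 10.2:

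1. Report the baseline distribution of item C by arm, and restrict the item C row to women scoring 2 at baseline, with that number as the denominator.
2. Drop *new* for this symptom.
3. Add an individual-level row: worsening in urge incontinence episodes per day on the diary at 6 and 12 months against baseline, with the threshold fixed before unmasking. The count has no fixed upper limit. Because SAP 13 already describes one analysis in the past tense, label the row post hoc if treatment assignments have been opened.
4. Reconcile the capture lists, the complications table and the worsening rule, so that it is clear whether urge incontinence is captured actively, by open-ended report or both, and how a report and an item response combine.

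A rise in UDI-irritative or OAB-q score is a poorer choice for this row, because neither is specific to urge leakage and the plan sets no threshold for individual worsening on either.

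The cost is SAP wording and a little programming, with no new data. The diary has no 3-month value, and day-to-day variation inflates the absolute rate, more so with a low threshold. Because participants are unmasked, that noise cannot simply be assumed equal in the two arms.
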